Protocol Abstract Page

A Phase 1/2 Open-Label Study of TPI 287 in Patients with Breast Cancer Metastatic to the Brain 2010-0198

Core Protocol Information

Study Chairman:	[name]
Department:	Breast Medical Oncology
[contact]
Unit:	1354
Full Title:	A Phase 1/2 Open-Label Study of TPI 287 in Patients with Breast Cancer Metastatic to the Brain
Protocol Phase:	Phase II
Version Status:	Terminated 04/18/2017
Version:	11
Document Status:	Final

Abstract

Objectives:

Primary objective (Phase 1)

To evaluate the maximum tolerated dose (MTD) and safety of TPI 287 administered once every three weeks in patients with refractory or recurrent breast cancer metastatic to the brain

Primary objective (Phase 2):

To estimate the efficacy of TPI 287 by assessing the overall response rate [ORR (CR + PR)] of recurrent brain metastases using the McDonald Criteria.

Secondary objectives (Phase 1 and 2):

- a. To evaluate response duration of breast brain metastases on TPI 287
- b. To evaluate rate and duration of the clinical benefit (CR+PR+SD)
- c. To assess activity of TPI 287 on extracranial metastatic disease
- d. To measure median progression free and overall survival of patients with metastatic breast cancer treated with TPI 287

Rationale: (Be as concise as possible)

The current study proposes to examine a novel microtubule inhibitor TPI 287 that has shown potency and efficacy in a number of taxane sensitive and resistant tumors in

both preclinical and clinical studies. TPI 287 has also been shown to be very well tolerated and exhibits limited myelosuppression at the currently employed doses. It has also been shown that IV TPI 287 can penetrate the brain parenchyma to reach pharmacologically and clinically relevant levels, which suggests that breast cancers metastatic to the brain would be an appropriate target for therapy. There is a significant amount of human safety data for TPI 287 with over 100 adult patients and now 5 pediatric patients who have received drug in prior clinical trials to adequately assess the safety of the clinical trial and the dosing regimen for TPI 287 planned.

A brain-tropic derivative of the MDA-MB-231 “triple negative” breast cancer cell line, 231-BR, has been used to test the efficacy of drugs administered systemically to mice with nascent and established brain tumors. In this assay, paclitaxel, ixabepilone and abraxane (all microtubule inhibitors) did not have significant inhibitory activity. TPI-287 at 18 mg/kg delivered on days 3, 7 and 11 significantly reduced the outgrowth of brain metastases (55% reduction, $p=0.028$), and reduced proliferation in brain metastases (16% reduction, $p=0.008$). Based on the results of this preclinical model, the utility of TPI 287 for the treatment of breast cancer metastatic to the brain is being explored in the clinical setting in this current protocol.

In a recent clinical pilot study in glioma patients at MD Anderson Cancer Center dosing at 185 mg/m² once every three weeks in combination with Avastin showed no dose limiting toxicity. In the initial version of this study, TPI 287 administered at a dose of 125 mg/m² showed no evidence of any toxicity when administered weekly for three out of every four weeks. However, since it was also suggested by other Phase 2 studies that higher concentrations administered once every three weeks may provide greater efficacy, this amendment provides for a higher starting dose to explore the MTD on this schedule and then to evaluate efficacy.

Eligibility: (List All Criteria)

Inclusion:

- 1) Patients must have histologically proven breast cancer with metastatic disease to the brain.
- 2) Patients must have measurable disease on MRI that has progressed after prior therapy. PD will be defined as a $\geq 25\%$ increase in the sum of the products of greatest perpendicular diameters of all measurable disease over the smallest sum observed (since treatment started) on Gd-MRI, the appearance of new lesions on scan, or clinical or neurologic worsening despite stable disease on the last 2 scans.
- 3) Patients may have had any number of prior surgeries, radiation and/or chemotherapy regimens as adjuvant, neoadjuvant or palliative therapy for the treatment of their disease
- 4) Patients must be ≥ 18 years of age.
- 5) Patients must have an ECOG performance status of 0, 1 or 2.
- 6) Patients must have adequate bone marrow function as evidenced by an absolute neutrophil count $\geq 1,500$ /microliters and a platelet count $\geq 100,000$ /microliter, adequate renal function as evidenced by

serum creatinine ≤ 2.0 mg/dL, adequate hepatic function as evidenced by serum total bilirubin ≤ 2.0 mg/dL, AST/SGOT and ALT/SGPT $\leq 3X$ the ULN.

7) Patients must have recovered and healed from the effects of any prior surgery, must have received prior chemotherapy at least 2 weeks prior to dosing with adequate recovery of WBC and platelet counts, and at least 12 weeks must have elapsed from the completion of radiotherapy, unless there are new lesions appearing on imaging within this 12 weeks frame.

8) Women of child-bearing potential (i.e. ≤ 50 years of age or has had menstrual cycle within the past 12 months, if > 50 years of age. If in doubt, check FSH, LH and estradiol level) must have a negative urine or serum pregnancy test at screening.

9) Sexually active patients must agree to use adequate contraception (abstinence or barrier contraceptives must be used throughout the trial and one month after end of treatment) for the duration of the study .

10) Patients or their legal representative must be able to read, understand and sign an informed consent form (ICF).

11) TPI 287 may interfere with coumadin dosing and patients who are taking this combination will require monitoring of their PT, PTT and INR.

Exclusion:

1) Patients who are receiving concurrent enzyme-inducing anti-epileptic drugs (EIAEDs) (e.g., carbamazepine, oxcarbazepine, phenytoin, fosphenytoin, phenobarbital and primidone) or who received EIAEDs within 2 weeks prior to the first dose of study drug.

2) Patients with uncontrolled intracranial hypertension syndrome (defined as: persistence of headache, transient visual obscurations, and/or diplopia despite optimal clinical management) or uncontrolled seizure activity (i.e. recorded despite optimal medical management).

3) Patients who are not on a stable or decreasing steroid dose for the previous week prior to the first dose of study enrollment

4) Patients who are taking bevacizumab or have taken bevacizumab within the past 2 weeks for treatment of their brain metastases

5) Patients with an active infection (i.e., clinical signs or symptoms, including, but not limited to: bleeding/pustulent skin infections; productive cough associated with fever) on antibiotics or with a fever $\geq 38.5^{\circ}\text{C}$ within 3 days prior to registration (i.e. date when the patient signs the consent and/or the patient is registered in CORE).

6) Patients with NYHA Class 3 or 4 congestive heart failure.

7) Patients with known HIV or Hepatitis B or C

8) Patients who are pregnant or lactating or not practicing adequate contraception

9) Patients with any other medical condition, including mental illness or substance abuse, deemed by the Investigator to be likely to interfere with the patient's ability to sign the ICF or his/her ability to cooperate and participate in the study, or to interfere with the interpretation of the results.

10) Patients who are receiving concomitant systemic therapy for breast cancer.

11) Patients with leptomeningeal disease (LMD) or with a history of LMD will be excluded.

Are patients <18 years of age eligible to participate in this study? Yes No

Studies that include children must meet the criteria for inclusion.

http://www.fda.gov/ohrms/dockets/AC/04/briefing/4028B1_05_NIH-Inclusion%20of%20Children.doc
<http://www.hhs.gov/ohrp/policy/populations/children.html>

Studies that exclude children must have appropriate justification. Please select all that apply:

Phase I or Phase II study targeting cancer that is very unusual in pediatrics (e.g., prostate, lung, breast, chronic lymphocytic leukemia, etc.)

Are participants >65 years of age eligible to participate in this study? Yes No

Are pregnant women eligible to participate in this study? Yes No

Will the recruitment population at M. D. Anderson include persons who are incarcerated at time of enrollment (e.g., prisoners) or likely to become incarcerated during the study?

Yes No

Disease Group:

Breast

Treatment Agents/Devices/Interventions:

TPI 287

Proposed Treatment/Study Plan:

Is treatment assignment randomized? Yes No

Is this a blinded or double-blinded study? Yes No

This is an open label, Phase 1/2, exploratory trial evaluating the efficacy and safety of TPI 287 in patients with refractory or recurrent brain metastases from breast cancer.

During Phase 1, the dose of TPI 287 will be escalated in sequential dose cohorts (inter-cohort dose escalation). TPI 287 will be administered at an initial dose of 160 mg/m² as a 60-minute (\pm 10 minutes) intravenous (IV) infusion once every three weeks (i.e., 1 cycle = 21 days). If patients enrolled at this dose have no dose limiting toxicities (DLTs) within 21 days of receiving the first dose of study drug, additional patients will be enrolled in subsequent cohorts of 3 patients at 20 mg/m² increments (180 mg/m², 200 mg/m², 220 mg/m², etc.) to explore a maximum tolerated dose (MTD) on this schedule for this patient population. If patients experience DLT at the starting dose, one dose level below (Level -1) is also proposed.

If 1 out of 3 patients experiences a DLT within 21 days of receiving the first dose of study drug, an additional 3 patients will be enrolled in that cohort. If \geq 2 patients at

any dose level experience DLT within 21 days of receiving the first dose of study drug, the MTD will be the previous dose level tested.

The MTD determination will be based on the number of patients that experience DLTs within 21 days of receiving the first dose of study drug. DLTs will be considered to be any hematologic toxicity \geq Grade 3 within 21 days of receiving the first dose of study drug that does not recover within 3 weeks or any non-hematological toxicity \geq Grade 3 within 21 days of receiving the first dose of study drug that does not improve to Grade 1 or baseline within 3 weeks

Patients on the Phase 2 portion of the study will be enrolled at the MTD determined during Phase 1. Initially, 25 patients will be enrolled in the Phase 2 portion of the trial; if at least 5 patients are shown to have an objective response, an additional 26 patients will be enrolled.

Patients may continue treatment in the study at any dose until intracranial disease progression or death, unacceptable toxicity, withdrawal of consent, or discontinuation based on Investigator discretion. Patients will be followed for survival for up to 1 year after enrollment on the study.

Intra-patient dose escalation will be allowed for patients with extracranial progressive disease as long as the response of intracranial disease is stable or better and there is no unacceptable toxicity. Only one dose escalation will be allowed per patient. The dose will be escalated to the next higher dose level (20 mg/m² increase); under the condition that this higher dose level was previously shown to be safe per the inter-cohort dose escalation criteria.

Table of Procedures and Assessments:

Event	Screen	Cycle 1			Cycle 2	Subsequent Cycles	Follow-Up Visit 28 ±2 days after last dose
		Day 1	Day 8	Day 15	Day 1		
Informed consent	X ²						
Medical & surgical history ^a	X ⁴						
Prior history and therapy for breast cancer ^b	X ⁴						
Demographics	X ⁴						
Physical examination ^c	X ⁴					X ³	X
Vital signs ^d	X ⁴	X				X ^{3, 6}	X
ECOG performance status	X ⁴	X ¹				X ¹	X
Laboratory Studies ^e	X ³	X ¹	X	X	X	X ¹	X
Urinalysis ^e	X ³						
Pregnancy test ^f	X ³						
Brain Gd-MRI ^g	X ²					X ⁷	X ³
Extracranial disease assessment ^g	X ²					X ⁷	X ³
Concomitant medications ^h	X ⁴	X ⁴				X	X
BSA calculation ⁱ		X ⁴				X ¹	
Administration of TPI 287 ^j		X ³			X ³	X ³	
AE monitoring ^k	X	X				X ¹	X
Survival ^l						X	X

Description/Definitions of Procedures and Assessments	Timing
a Complete medical and surgical history to include pertinent medical conditions and a careful history of all prior medical treatments	1 Prior to dosing with study drug within 7 days of each cycle unless otherwise specified
b Complete history of breast cancer to include date of diagnosis, histologic evidence of disease, dates of prior therapies (including surgery, radiation, chemotherapy) as well as date of documented recurrence/progression	2 Within 28 days of first dose of study drug
c Physical examination (including height and weight), noting all baseline abnormalities including neurologic exam	3 Within 14 (\pm 3 days) of first dose of study drug
d Temperature, pulse rate, blood pressure (sitting)	4 Within 7 days (\pm 3 days) days of dose of study drug
e Complete blood count, including RBC, MCV, MCH, MCHC, hemoglobin, hematocrit, WBC with differential, and platelet count (WBC with differential and platelets will be collected weekly for 1 st cycle and within 7 days of each subsequent cycles); additional labs to be obtained at these time include sodium, potassium, chloride, bicarbonate, calcium, glucose, BUN, creatinine, albumin, total protein, alkaline phosphatase, total bilirubin, ALT, AST; Dipstick determinations of urinary protein, glucose, ketones, hemoglobin, and bilirubin, but only for the first three cycles and/or if clinical indicated. Patients who are taking coumadin (warfarin) will have PT, PTT, and INR prior to each cycle of treatment. Patients who have 2+ or greater hemoglobin or protein on a spot urine must have a microscopic examination performed. Urine exam is done only at screening.	5 Prior to dosing as interim update (only note changes from prior record). To be obtained within \pm 3 days.
f For females of childbearing potential only, may be based on serum or urine testing	6 Prior to dosing with study drug and immediately following 60 minute infusion
g Brain Gd-MRI must be obtained as per protocol. Extracranial disease assessments may include CT/MRI scans of chest, abdomen, pelvis as well as bone scans, and as per standard of care otherwise indicated by treating physician. All disease assessments will be performed when clinically indicated.	7 Within 7 days prior to odd numbered cycles
h All medications/therapies used within 30 days prior to first dose of study drug	8 If scan has not been obtained within previous 2 cycles
i If weight fluctuates \pm 10% from prior measurement, new BSA will be used to calculate next dose	9 Within (\pm 1 day)
j One hour IV infusion of TPI 287 Injection on day 1 every 21 days. See Section 5 for Study Drug Administration.	
k All drug-related toxicities must be followed for resolution. Patients are to be followed for up to 30 days (\pm 5 days) after last drug administration for adverse events, regardless of causal relationship.	
l Data will be collected every 3 months from the time the patient is off-treatment up to a period of 1 year from the patient's date of enrollment	

* Note that the timing of assessments may be varied by reasonable adjustments to the times indicated for scheduling or logistical issues. Patients whose on study laboratory tests were done > 7 days prior to starting treatment and whose clinical condition has changed between the time of these tests and the initiation of treatment will have a repeat chemistry panel prior to the start of treatment.

Dose Levels:

Level	Dose of TPI 287 (mg/m²)
Level - 1	140
Starting dose/Level 1	160
Level 2	180
Level 3	200
Additional dose level increases in 20 mg/m² increments	

CTCAE version 4 will be utilized in this protocol.

Study Enrollment:

The study population for this research will consist of participants from:

Only at MDACC

Estimated Accrual:

Total Accrual at MDACC: 69
 Estimated monthly accrual at MDACC: 0-1

Accrual Comments:

All patients will be accrued MD Anderson Cancer Center

Is this an NCI-Cancer Therapy Evaluation Protocol (CTEP)? No

Is this an NCI-Division of Cancer Prevention Protocol (DCP)? No

Statistical Considerations:

This is an open label, Phase 1/2, exploratory trial evaluating the efficacy and safety of TPI 287 in patients with refractory or recurrent brain metastases from breast cancer.

The primary objective of the Phase 1 portion of the study is to determine the MTD of TPI 287 and in the Phase 2 portion of the study whether TPI 287 can provide clinical benefit for patients with metastatic breast cancer to the brain following failure of prior therapy, as measured by overall response rate.

TPI 287 will be administered intravenously at an initial dose of 160 mg/m² once every three weeks. Dose escalation will continue in cohorts of 3 patients who will receive increasing doses until 1 out of 3 experience a dose limiting toxicity (DLT) at which time an additional 3 patients will be added at that dose. If ≥ 2 patients experience a DLT, the MTD will be considered the prior dose level. Dose levels will be 160 mg/m², 180 mg/m², 200 mg/m² and then increased in 20 mg/m² increments until the MTD is reached.

Once the MTD has been reached an initial cohort of 25 patients will be enrolled; if at least 5 patients are shown to have an objective response, an additional 26 patients will be enrolled.

The following data sets will be used in this study:

- All enrolled and eligible subjects (ITT) population: All eligible subjects who signed the informed consent form.
- All treated and eligible patients (Safety and Efficacy evaluable) population: All patients who received at least one dose of study drug

Efficacy analyses will be performed on the Safety and Efficacy evaluable population in the patients on Phase 2. Safety analysis will be performed on the Safety and Efficacy evaluable population in both portions of the study.

The primary outcome measure will be response rate in the Phase 2 portion of the study. A two-stage patient accrual plan is used for this portion. Based on historical data, responses to chemotherapy in this disease ranged from approximately 30 to 55%; however in most cases these were combined with whole brain radiation therapy. Therefore, a 15% response rate to single agent

chemotherapy will be targeted as a reasonable outcome for this patient population. We target this response rate of 15% because our experience in this heavily pre-treated patient population indicates that almost none of the patients of the patients will respond under the current best-supportive care/hospice care regimen. We used trial and error to get a two-stage design with reasonable operating characteristics for $p_0 = 15\%$. One such design would have 25 patients in the first stage and 26 patients in the second stage. It would continue onto the second stage if more than 4 patients had response in the first stage. The trial would be considered a success if 11 or more out of the total 51 patients had response. This trial has a false positive (alpha) rate of 11% (under $p_0 = 15\%$) and a false negative (beta) rate of 12% (under $p_1 = 30\%$). The trial also has a probability of early termination under p_0 (i.e., if the true response probability is $p_0 = 15\%$) of 68%.

Data Safety Monitoring Board / DSMB at MDACC:

Select the name of the data safety monitoring board (DSMB) monitoring this protocol:
Not Applicable

Please explain:
This study open label and not randomized.

Protocol Monitoring:

Does this protocol have a schedule for interim and final analysis? No

Provide a rationale for no interim analysis.

This is not a randomized study.

Protocol Monitoring Plan:

The protocol will be monitored by MDACC IND office

Intellectual Property:

1. Does this study include any agents, devices, or radioactive compound (or drug) manufactured at MD Anderson Cancer Center or by a contract manufacturer? No

Investigational New Drugs (IND):

Does this protocol require an IND? Yes

Who is the IND Holder/Regulatory Sponsor?

MDACC

IND Number: 106,771

Please "Compose" an Investigator's Brochure Cover Letter. For technical assistance, contact the PDOL

Help Desk, [contact].

Investigational Device (IDE):

Does this study utilize an Investigational Device? No

Sponsorship and Support Information:

Does the Study have a Sponsor, Supporter or Granting Agency? Yes

Sponsor Name: Cortice Biosciences Inc.
Support Type: Industry Funding
Agent Name(s): TPI 287

This Sponsor/Supporter/Granting Agency will receive data.

Radioactive Material:

Does this study involve the administration of radioisotopes or a radioisotope labeled agent? N/A

[Click here for help](#)

Biosafety:

Does this study involve the use of Recombinant DNA Technology? No

Does this study involve the use of organisms that are infectious to humans? No

Does this study involve human/animal tissue other than blood derived hematopoietic stem cells? No

Questions should be addressed to the Transfusion Medicine Tissue Coordinator at [contact].

Laboratory Tests:

Is there any biomarker testing in this study being used to determine patient/participant eligibility, treatment assignment, or management of patient/participant care?

Yes

No

[Not Applicable For This Protocol](#)

Manufacturing:

Will you manufacture in full or in part (split manufacturing) a drug or biological product at the M. D. Anderson Cancer Center for the proposed clinical study? No

Student/Trainee Information:

Is this research being conducted as a partial fulfillment for completion of a degree? No

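### The baseline brain MRI need not follow the last dose of prior systemic therapy, so in a narrow group of patients another agent's effect could be counted as a TPI 287 response

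*Combined protocol and SAP*

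**What the plan says.** All references are to the combined protocol and SAP.

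- **Baseline scan.** In the Table of Procedures and Assessments, the screening Brain Gd-MRI carries timing note 2: "Within 28 days of first dose of study drug". No MRI is marked for Cycle 1 Day 1.
- **On-study scans.** Timing note 7 reads "Within 7 days prior to odd numbered cycles" and is attached to the Subsequent Cycles column.
- **Chemotherapy.** Under inclusion 7, patients "must have received prior chemotherapy at least 2 weeks prior to dosing".
- **Bevacizumab.** Exclusion 4 removes "Patients who are taking bevacizumab or have taken bevacizumab within the past 2 weeks for treatment of their brain metastases". It does not say from which date the 2 weeks are counted.
- **Ongoing therapy.** Exclusion 10 removes "Patients who are receiving concomitant systemic therapy for breast cancer".
- **Progression.** Inclusion 2: "Patients must have measurable disease on MRI that has progressed after prior therapy".
- **Medication record.** Note h to the table captures "All medications/therapies used within 30 days prior to first dose of study drug".

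The Phase 2 primary endpoint (Objectives) is intracranial CR + PR by the McDonald criteria. Statistical Considerations analyses it in all Phase 2 patients who received at least one dose. The trial continues with at least 5 responses in 25 and succeeds with at least 11 in 51.

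**The concern.** With no control arm, the response rate measures drug activity only if the change since the baseline scan is due to the study drug. Two features of the eligibility and scan-timing rules weaken that.

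First, the baseline scan may be older than the last dose of prior chemotherapy. A patient scanned on day -27 and given another agent on day -20 satisfies both timing rules, and response is then measured from a scan that predates that agent.

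Second, the criteria on recent bevacizumab do not fit together. Exclusion 4 is limited by the reason for use, exclusion 10 by therapy still being received, and inclusion 7 by the word chemotherapy. Bevacizumab given for extracranial disease and stopped a few days before dosing is not clearly caught by any of them. Since the plan excludes recent bevacizumab when given for brain metastases, it evidently treats such exposure as a problem. Any effect on the brain scan would not depend on why the drug was given.

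At stake are the two decisions that rest on response counts: continuing to stage 2 and declaring success.

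**Working it through.** **Timing.** The baseline scan may be as early as day -28 (timing note 2), and chemotherapy is allowed until day -14 (inclusion 7). The overlap is 28 - 14 = 14 days in which a prior agent may be given after the baseline scan. Exclusion 4 gives the same figure for bevacizumab used for brain metastases, if its 2 weeks are counted back from first dose. For bevacizumab used for another reason, exclusion 4 sets no interval. If inclusion 7 is also read as not covering it, the open period could extend to about 28 days.

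**Reproducing the stated design.** Inputs from Statistical Considerations: 25 patients in stage 1, 26 in stage 2, continue with at least 5 responses, succeed with at least 11 of 51, p0 = 15%, p1 = 30%.

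P(success | p) = sum over x = 5 to 25 of P(X1 = x) × P(X2 ≥ 11 - x), with X1 ~ Bin(25, p) and X2 ~ Bin(26, p).

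- p = 0.15: 0.1068, so alpha is 10.7% (stated 11%).
- p = 0.30: 0.8763, so beta is 1 - 0.8763 = 12.4% (stated 12%).
- Early termination at p = 0.15: P(X1 ≤ 4) = 0.6821 (stated 68%).

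The plan's figures are correct.

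**Effect of misattributed responses.** Let f be the share of true non-responders scored as responders because of a prior agent. At a true rate of 15%, the observed rate is p = 0.15 + 0.85f. The documents give no value for f, so a range is shown.

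| f (assumed) | p | P(continue) | P(success) |
|---|---|---|---|
| 0 | 0.1500 | 31.8% | 10.7% |
| 0.5% | 0.1543 | 34.0% | 12.3% |
| 1% | 0.1585 | 36.3% | 14.1% |
| 2% | 0.1670 | 40.8% | 18.1% |
| 5% | 0.1925 | 54.2% | 32.7% |

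f is the share of patients exposed after the baseline scan multiplied by the chance that such exposure alone yields a scored response. For example, 0.5% = 5% × 10%, 2% = 10% × 20%, and 5% = 25% × 20%.

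**Dependence on the base rate.** If TPI 287 were wholly inactive (true rate 0) and f were 5%, then p = 0.05. P(continue) is then 0.7% and P(success) about 0.003%. Carry-over alone would not make the trial succeed; the bias matters when the true rate is near p0.

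**Scan timing.** Cycles last 21 days, so Cycle 3 Day 1 is day 1 + 2 × 21 = day 43. The first scheduled response scan falls on about days 36 to 43. Chemotherapy last given on day -14 would then be about 50 days in the past (36 + 14).

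**The case against.** Several counterpoints carry weight.

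- **Inclusion 2 narrows the route.** A further cycle of a regimen on which the disease has just progressed is unlikely to produce a response. What remains is mainly a different agent, started after the scan and stopped before dosing. This stands, and it is why the group should be small. It does not close the route: the criterion does not say after the most recent therapy, and it accepts clinical or neurologic worsening with stable scans.
- **The first response scan is late.** At about days 36 to 43, a short-lived effect may have gone. This also stands, but tumour shrinkage from another agent between the baseline scan and dosing could still be present.
- **Direction.** A reader might infer that the bias always favours TPI 287. It does so only when the prior agent is given after the baseline scan. If bevacizumab was already reducing enhancement at that scan, the lesions would be understated, and their later return would count against TPI 287.
- **Bevacizumab for extracranial disease.** A reader might infer that the plan lets it continue on study. It does not: exclusion 10 bars ongoing systemic therapy for breast cancer. For recently stopped bevacizumab, inclusion 3 groups prior treatment as surgery, radiation and chemotherapy, so inclusion 7 could be read to cover it. The text is ambiguous rather than plainly open.
- **Incomplete source.** The document is headed as a protocol abstract, and note g refers to the protocol for the MRI. The missing ordering rule is established only for the supplied text.

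**Conclusion.** The point holds in limited form. On the supplied text, following the plan exactly permits a response baseline that predates a prior agent by up to 14 days under the chemotherapy rule, and nothing in the analysis identifies or handles such patients. The three criteria on recent bevacizumab do not clearly agree.

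The size is unknown. P(success) of 12.3% to 32.7%, against 10.7%, rests on assumed f of 0.5% to 5% and on a true rate of 15%. A reader might infer that the real false positive rate is near 33%. The documents do not support that: the top of the range needs something like a quarter of patients exposed after the scan and a fifth of those converted, and inclusion 2 makes such exposure uncommon. With f = 0, the stated alpha is correct. This is a question of attributing responses, not an error in the sample size, and it is worth correcting because the correction is cheap.

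**What to change.** 1. Require the Gd-MRI used as response baseline to be acquired after the last dose of any prior systemic anticancer therapy, including bevacizumab for any indication, within the existing 28-day window.
2. Report a sensitivity ORR in which any patient whose baseline scan precedes the last prior dose counts as a non-responder. The 30-day medication record in note h spans the whole 28-day window, so no new data are needed. The version status is given as terminated; if enrolment is over, this analysis can still be done.
3. Reconcile exclusion 4, exclusion 10 and inclusion 7 on recently stopped bevacizumab, and state the date from which exclusion 4 counts. Which interval applies, and to whom, is a clinical decision for the sponsor and investigator; none is proposed here.

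The cost is small: a few patients would need their screening MRI timed later, and one sensitivity analysis is added. The scan rule does not remove a delayed effect of a drug given before the scan, nor the opposite bias from bevacizumab still acting at baseline.

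### Phase 1 DLTs depend on recovery within 3 weeks, but the printed schedule and the 21-day escalation gate do not fit that definition

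*Combined protocol and SAP*

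**What the plan says.** All references are to the Combined protocol and SAP.

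- **DLT definition (Proposed Treatment/Study Plan).** A hematologic DLT is a toxicity of at least "Grade 3 within 21 days of receiving the first dose of study drug that does not recover within 3 weeks". A non-hematologic DLT has the same onset window and must fail to return to Grade 1 or baseline within 3 weeks. The text does not say when the 3 weeks start.
- **Gate (same section).** "The MTD determination will be based on the number of patients that experience DLTs within 21 days of receiving the first dose of study drug". With no DLT in that time the next cohort of 3 opens. One in 3 adds 3 patients, and two or more make the previous level the MTD. Intra-patient escalation requires that the "higher dose level was previously shown to be safe per the inter-cohort dose escalation criteria".
- **Table of Procedures and Assessments.** The row "AE monitoring ^k" is marked at Screen, Cycle 1 Day 1, Subsequent Cycles and Follow-Up. It is blank at Day 8, Day 15 and Cycle 2 Day 1. Laboratory studies are marked in all seven visit columns.
- **Note e.** "WBC with differential and platelets will be collected weekly for 1 st cycle and within 7 days of each subsequent cycles".
- **Note k.** "All drug-related toxicities must be followed for resolution". It also requires AEs of any cause to be followed to 30 (±5) days after the last dose.
- **Timing note 1**, attached to the Subsequent Cycles cells for AEs and laboratory studies: "Prior to dosing with study drug within 7 days of each cycle unless otherwise specified".

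**The concern.** Classifying a DLT takes two observations: that the toxicity reached Grade 3 in the first 21 days, and whether it had recovered when the 3 weeks ran out. For toxicities that are not laboratory values, the printed table schedules neither. For blood counts it schedules the first but, if the clock starts at onset, not reliably the second. The gate is also set at 21 days, when a toxicity that arose during those days may still be inside its recovery period.

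The MTD is the Phase 1 primary objective and sets the Phase 2 dose. In cohorts of 3, one patient changes the action: 0 of 3 escalates, 1 of 3 expands, and a second DLT stops. An uncounted event pushes towards a higher dose. A recovery that cannot be dated can be called either way.

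**Working it through.** The plan states no figure that depends on this schedule, so there is none to reproduce. The check is a day grid.

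**Inputs.** Day 1 is the first dose and a cycle is 21 days (Proposed Treatment/Study Plan). With no delay, Cycle 2 Day 1 is 1 + 21 = Day 22 and Cycle 3 Day 1 is Day 43. Laboratory studies fall on Days 1, 8, 15 and 22, then within 7 days before Cycle 3, which is Days 36–43 (table, note e, timing note 1).

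**1. When the recovery period closes.** Three starting points are possible:

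- From first dose: 1 + 21 = Day 22. The Day 22 count settles a cytopenia.
- From the end of the onset window: 21 + 21 = Day 42. The pre-Cycle 3 draw (Days 36–43) can serve.
- From onset on day t: t + 21, so onsets on Days 1–21 close on Days 22–42.

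Only the last reading opens a gap in the counts. It is also the only one that gives every patient the same 3 weeks to recover.

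**2. Blood counts, onset clock, patient redosed on Day 22.** The next draw comes 36 − 22 = 14 to 43 − 22 = 21 days after Day 22.

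| Grade 3 or higher first seen | Deadline | Counts after onset, up to Day 22 | Days of the 36–43 window on or before the deadline | Next draw after the deadline by |
|---|---|---|---|---|
| Day 8 | 8 + 21 = 29 | Days 15, 22 | 0 of 8 | 7 to 14 days |
| Day 15 | 15 + 21 = 36 | Day 22 | 1 of 8 | 0 to 7 days |
| Day 22 | 22 + 21 = 43 | none | 8 of 8 | not after |

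A count that has recovered by Day 22 is settled. One still abnormal on Day 22 after first appearing on Day 8 or Day 15 may not be.

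**3. Patient not redosed.** The follow-up visit, 28 ± 2 days after the Day 1 dose, falls on Days 27–31 and carries both laboratory studies and AE monitoring. It supplies a reading inside the gap.

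**4. Non-laboratory toxicity.** Scheduled AE checks on Days 2–22 number 0 as printed, or 1 (somewhere in Days 15–22) if Cycle 2 counts as a subsequent cycle. Take a Grade 3 event starting on Day 8 that is Grade 2 on Day 22 and still Grade 2 on Day 29. It has not reached Grade 1 by its deadline, so (unless Grade 2 was its baseline) it is a DLT. As printed, the next AE check for a redosed patient is on Days 36–43, 7 to 14 days past the deadline, and both the Grade 3 peak and the Day 29 status must be reconstructed. With one check before Cycle 2, the patient may show only Grade 2.

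**5. The gate.** On the onset clock the earliest closing day is 1 + 21 = Day 22. At the end of Day 21, an ongoing Grade 3 toxicity that could still recover is not yet a DLT. The supplied text states no wait for it.

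**The case against.** The strongest reply is that a true DLT must persist. On the onset clock it is still unrecovered on Day 22, when the patient attends for laboratory studies and the second dose. An event that came and went between Day 8 and Day 15 is not a DLT, so missing it does no harm. This largely stands. It fails where the event is still present but has dropped to Grade 2: it remains a potential DLT, yet nothing on Day 22 shows that it was once Grade 3.

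Note k is attached to the AE row and requires follow-up to resolution, plus all-cause follow-up that runs to Days 47–57 after a Day 22 dose. A reader might infer from the blank cells that AEs go uncollected, or that the schedule fails to observe DLTs at all. The documents do not support that: note k applies between visits, and laboratory onset is observed on Days 8, 15 and 22. What note k lacks is an interval and any link to the 3-week limit.

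The table may not have been read cleanly. Several other rows are also blank at Cycle 2 Day 1, and note e appears to use subsequent cycles for everything after the first. The Cycle 2 blank may therefore be layout. The Day 8 and Day 15 blanks do not depend on this.

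Finally, note j points to a Section 5 for drug administration that is not in the supplied text. Hold and delay rules may sit there. It cannot be inferred that the full protocol allows redosing or escalation over an unresolved Grade 3 toxicity, only that the supplied text states no hold.

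**Conclusion.** The point holds as a mismatch between a DLT definition that needs 3 weeks of non-recovery and a schedule and gate built around 21 days. It has three parts:

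- Non-laboratory events that peak at Grade 3 and settle at Grade 2 may go uncounted.
- Recovery of cytopenias first seen on Day 8 or Day 15 may go undated in patients redosed on time.
- The next level can open on an unclassified toxicity.

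The second part rests on the onset clock and on no dose delay. The first rests on the AE row as printed. The third rests on the supplied text alone.

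A reader might go on to infer that the MTD is set too high by some stated probability. The documents give no rate of missed events, so no such figure can be derived. No stated sample size or error rate changes. This is a cheap improvement of minor to moderate severity.

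**What to change.** For Phase 1 patients:

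1. Mark AE monitoring at the existing Day 8, Day 15 and Cycle 2 Day 1 visits.
2. State in the DLT definition that the 3 weeks run from onset.
3. In notes e and k, require any Grade 3 or higher toxicity that arose in the onset window and is unresolved at Cycle 2 Day 1 to be re-graded weekly, by CBC or AE grade, until it recovers or reaches its deadline, with a reading on the closing day.
4. Do not open the next level, or allow intra-patient escalation that relies on the current one, until that toxicity is classified. For onsets on Days 1–21 this is at most Day 42.

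**Cost.** An amendment to one table row, two notes and the DLT and escalation text. No new routine visits are needed. If Phase 1 takes 69 − 51 = 18 patients (total accrual less the full Phase 2 number), the added AE checks number 18 × 3 = 54. Re-grading applies only to patients unresolved at Cycle 2 Day 1 and adds at most about three readings each (for example Days 29, 36 and 42). The real downside is an occasional wait before the next level opens, up to 42 − 21 = 21 days.
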